2.2 Secondary objectives

- To develop the conceptual framework for mass-based objective functions for inverse planning optimization of radiotherapy treatments.
- To study different forms of mass-based objective functions.

3.0 PATIENT SELECTION

3.1 Inclusion Criteria

- Patients must have histologically confirmed head-and-neck, lung, or prostate tumors.
- Patients who will be treated with radiation therapy or concurrent chemoradiation therapy.
- Gross Tumor Volume (GTV) or resection cavity must be visible on CT such that it can be delineated as a target for radiotherapy.
- Patients who are able to understand the investigational nature of this study and agree to sign a written informed consent document.

3.2 Exclusion Criteria

- Pregnant or nursing women will not participate. Women of reproductive potential must be offered a pre-treatment pregnancy test and informed of the need to practice an effective contraceptive method during the therapy.
- Patients younger than 18 years.
- Patients whose size and weight would not allow CT scanning.

No vulnerable populations (fetuses, pregnant women, children, prisoners) will be included in this study.

3.3 Enrollment and Withdrawal

3.3.1 Enrollment Guidelines

Study enrollment, as used in this protocol, will be defined as the investigator's confirmation of the subject's eligibility by signing an eligibility checklist.

3.3.2 Withdrawal Guidelines

Patients can withdraw at any time if they decide to do so. If, for any reason, the attending radiation oncologist decides that patient participation in the study is not in their best interest the subject will be withdrawn from the study. Furthermore, if the PI decides to discontinue the study, subjects' participation will end. Patients who are enrolled on study but not treated will be excluded from all analyses.

4.0 RESEARCH PLAN

To support both currently planned and future investigations, a patient database will be established to manage the CT imaging data acquired through this protocol as well as other relevant data such as MRI and/or PET-CT studies. All analyses in this study will be based on this database.

4.1 Assessment of Protocol Eligibility and Enrollment

Eligible patients will be pre-screened by the attending physicians. If the patient is deemed suitable, informed consent will then be obtained.

4.2 Treatment Planning for Therapy Purposes

This protocol is a non-therapeutic protocol. Therefore, patients enrolled in this protocol will be treated according to the standard of care for IMRT, VMAT, and SRT.^{29, 97, 138-144} Treatment planning will be performed with any combination of coplanar or non-coplanar IMRT fields or VMAT fields, to deliver the specified dose while restricting the dose to the normal tissues. Field arrangements will be determined to produce the optimal plan in accordance with volume definitions. The treatment plan used for each patient will be based on analyses of the volumetric dose, including DVH analyses of the planning target volumes (PTVs) and critical normal structures, as well as evaluation of isodose curves and isodose volumes. In addition to the abovementioned analyses (which is according current standard of care) our study will evaluate the pertinent DMHs and isomass volumes for all anatomical structures of interest.

In addition to the planning CT scan and/or pre- and post-treatment MRIs and/or PET-CTs done routinely as part of standard of care, patients enrolled in this protocol will undergo two additional CT imaging studies at different times during the treatment course. CT studies are the primary data source for any type of external beam treatment planning. The information gained from the repetitive CT scans will be used to quantify the volumetric and mass changes of soft tissue (e.g. tumor shrinkage). Furthermore, the data will be used to assess the relation among soft tissue changes and radiographic features as well as dose-mass and dose-volume histograms, as well as the time-trends for DVHs and DMHs.

All head-and-neck patients will be immobilized using custom-fabricated thermoplastic face masks affixed to the couch. Lung and prostate patients would be immobilized in body immobilization bags such as Alpha Cradles and vacuum immobilization bags (or vac-bags). Patients will be immobilized in the intended treatment position and imaged with a CT scanner in the same way as for standard 3DCRT and IMRT/VMAT/SRT treatment planning. The final decision for treatment immobilization devices will be left to the discretion of the attending physician.

4.3 CT Exam Specifications

All imaging studies for this protocol will be carried out at our Siemens 16 slice CT scanner in the Department of Radiation Oncology, Sylvester Cancer Center (SCCC)/SCCC_West/Deerfield Beach/new centers at the University of Miami. All subjects enrolled in this study will undergo four high-resolution CT scans. Head-and-neck and prostate patients will undergo three-dimensional (3D) CT scans, while lung patients will undergo time-resolved four-dimensional (4D) CT scans. 4D CT scans

allow capturing of the anatomical changes due to human breathing. These studies are required for thoracic/abdominal cancers since patient's anatomy changes significantly (on the order of 4-5 seconds) during a course of radiation. We will evaluate the effect of these changes on the calculated radiation dose. If applicable, i.e. requested by the attending radiation oncologist for therapeutic purposes according to the standard of care, the CT exam(s) may use the administration of radiocontrast.

Note that if the attending physician orders a CT scan throughout the course of treatment and/or at the follow-up or at least 6 weeks after completion of therapy as a standard of care, this CT imaging would be used in our research instead of exposing the subjects to additional CT scan for the sole purpose of this protocol. If the midway scan or post treatment scan, as ordered by the attending physician, are performed in the Radiology Department we would transfer the imaging data from PACS to our research treatment planning system for the purposes of this research.

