2.0 STUDY OBJECTIVES

2.1 Primary objectives

- To study and evaluate whether DMHs are better suited for predicting radiotherapy response and/or complication (toxicity) than standard of care realized through DVHs.
- To investigate the time-trending changes between patient anatomy and DMH inverse radiotherapy optimization.

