4.6 Duration of Study

Several CT volumetric studies will be performed for each enrolled subject: one before the radiotherapy course for patient treatment planning purposes (as part of the standard of care), one during the radiotherapy treatment course (between fraction 10 and 20 for 3DCT, IMRT or VMAT patients and after fraction 3 for SBRT patients), and one at follow up visit or at least 6 weeks post-radiotherapy treatment(whichever comes first). The acquisition of these imaging data will require approximately 15 additional minutes of the patient time at those visits.

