8.4 POTENTIAL RISKS

The CT imaging studies proposed in this study do not subject patients to any therapeutic intervention beyond what is prescribed as part of their routine clinical care. A synopsis of radiation doses from the proposed imaging studies to be delivered to each subject enrolled in this protocol is presented in Table 1. The data outlines the CT imaging dose from a single CT scan. This data is for a 4D CT scan. 4D CT scans deliver more radiation than much more commonly used 3D CT scans. Therefore, the presented dose estimates are effectively for upper dose limits. 4D CT scanning is relevant only for lungs patients. For head-and-neck and prostate patients standard 3D CT protocols will be used. As mentioned above, the 3D CT scans result in somewhat lower radiation doses than those outlined in Table 1.

Table 2 presents the data for cone beam CT (CBCT) and on-board imagers (OBI), used on daily basis for patient positioning and pre-treatment localization. The cumulative doses in the table are calculated for a standard 35 session course of treatment, aiming to deliver radiation dose between 6600 cGy and 7000 cGy (depending on the fractional dose) to the tumor(s). In those 35 treatments there will be 7 CBCTs (once per week), while the remaining 28 treatments will utilize OBI for patient positioning. If a patient undergoes a SRT treatment, then all 3 to 5 fractions (which comprise this treatment) will require the use of CBCT.

The risk to the participants in our prospective CT data collection is very minimal. The therapeutic doses delivered to cancer patients are of the order of 200 cGy in each daily fraction. It is evident from Table 1 that imaging dose of ~4 cGy, delivered through a 4D CT scan, is ~ 2% of that daily dose. Notably, 2% daily variation in the radiation output is within the operational specifications of modern linear accelerators. In other words the added imaging dose per one CT scan will be no larger than the stochastic variation of the daily machine output. Furthermore, Table 2 demonstrates that the dose resulting from 7 CBCT and 28 OBI applications, used as standard of care for accurate patient daily localization, is equivalent to four 4D CT studies, i.e. one more study than the proposed number in this protocol (we will subject patients to one CT which is standard of care and two more for research purposes).

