APPENDIX I:

TABLE 1: STANDARD FRACTIONATION CALENDAR

Assessment	Prior to RT	Between fractions 10 and 20	Follow up visit or at least 6 weeks post-RT (whichever comes first)
History & Physical Exam	X		X
MRI and/or CT studies (if applicable)	X		X
3D/4D CT scan	X	X	X

TABLE 2: SBRT CALENDAR

Assessment	Prior to RT	Between fraction 3 and fraction 4 of RT	Follow up visit or at least 6 weeks post-RT (whichever comes first)
History & Physical Exam	X		X
MRI and/or CT studies (if applicable)	X		X
3D/4D CT scan	X	X	X

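### Study CTs are counted as four and as three, added scans as three and as two, and a 3-fraction SBRT course has no slot for the mid-course scan

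*Combined protocol and SAP*

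**What the plan says.** **Total number of CTs.** Section 4.3 sets the requirement: "All subjects enrolled in this study will undergo four high-resolution CT scans". Section 4.6 lists three scans. The first is the planning CT. The second falls during treatment, timed "between fraction 10 and 20 for 3DCT, IMRT or VMAT patients and after fraction 3 for SBRT patients". The third is "one at follow up visit or at least 6 weeks post-radiotherapy treatment", whichever comes first. Both calendars in Appendix I mark the same three. Section 8.4 counts one standard-of-care CT and two research CTs, and describes four as one above the protocol's number.

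**Number added.** Sections 4.2 and 4.4 and the risk text of 8.4 say two. The summary sentence at the end of 8.4 speaks of adding three scans and puts their dose at 6% of one daily fraction and below 0.2% of the prescription.

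**Substitution.** Section 4.3 adds that where the physician orders a CT as standard of care, "this CT imaging would be used in our research instead of exposing the subjects to additional CT scan". The same note begins a sentence: "If the midway scan or post treatment scan, as ordered by the attending physician, are performed in the Radiology Department". It names no other scan after planning.

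**SBRT timing.** Appendix I, Table 2, puts the mid-course scan "Between fraction 3 and fraction 4 of RT". On stereotactic courses, section 8.4 says that "all 3 to 5 fractions (which comprise this treatment) will require the use of CBCT".

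**The concern.** Repeat CT is the procedure that this non-therapeutic protocol adds to standard care, so its mandatory number should have a single value. Read literally, section 4.3 obliges every subject to have a fourth scan that neither calendar places. The dose summary in 8.4 rests on a count of added scans that disagrees with three other places.

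The SBRT slot matters for a different reason. One of the two primary objectives is "To investigate the time-trending changes between patient anatomy and DMH inverse radiotherapy optimization", and section 4.2 says the repeat scans supply the data on change over time. If the mid-course scan cannot be taken in its stated slot, that time point is either missing or becomes a post-treatment scan for the patients affected.

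**Working it through.** **1. Counts, section by section**

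| Place | Total CTs | Added to planning CT |
|---|---|---|
| 4.2 | 1 + 2 = 3 (implied) | 2 |
| 4.3, requirement | 4 | not stated |
| 4.3, substitution note | planning + midway + post-treatment = 3 | 2 (implied) |
| 4.4 | not stated | 2 |
| 4.6 | 1 + 1 + 1 = 3 | 2 (implied) |
| 8.4, risk text | 1 + 2 = 3 | 2 |
| 8.4, comparison with positioning imaging | 4 − 1 = 3 | not stated |
| 8.4, summary | not stated | 3 |
| Appendix I, both calendars | 3 | 2 (implied) |

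The summary in 8.4 can be read in two ways.

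- *Three scans beyond planning.* This agrees with the four in 4.3 (1 + 3 = 4) and contradicts the 1 + 2 found elsewhere.
- *Three scans including planning.* This agrees with 1 + 2 = 3. The scans are then not all additions, and the 6% describes all study CTs rather than the added ones.

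**2. Dose**

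Inputs, all from section 8.4: about 4 cGy per 4D CT; 200 cGy per fraction; 6600 to 7000 cGy per course; highest 4D value in Table 1, 3.5 cGy. Formula: share = number of scans × dose per scan ÷ reference dose.

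The printed figures reproduce with three scans: 3 × 4 = 12 cGy; 12/200 = 6.0%; 12/7000 = 0.171% and 12/6600 = 0.182%, both below 0.2%.

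| Scans counted | Dose per scan | Sum | Share of 200 cGy | Share of 7000 to 6600 cGy |
|---|---|---|---|---|
| 2 | 4 cGy | 8 cGy | 4.0% | 0.114% to 0.121% |
| 3 | 4 cGy | 12 cGy | 6.0% | 0.171% to 0.182% |
| 2 | 3.5 cGy | 7.0 cGy | 3.5% | 0.100% to 0.106% |
| 3 | 3.5 cGy | 10.5 cGy | 5.25% | 0.150% to 0.159% |

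For two or three added scans, the printed 6% equals or exceeds the computed share, and the 0.2% bound holds in every row. These are upper bounds on research exposure, because a clinically ordered CT may replace a study CT. As a total rather than an added dose, all four CTs of section 4.3 would give 4 × 4 = 16 cGy, which is 8.0% of a fraction and 0.229% to 0.242% of the course.

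**3. SBRT slot**

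A course of k fractions has k − 1 intervals between fractions.

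- k = 3: intervals 1–2 and 2–3. There is no interval 3–4, and after fraction 3 the course is over.
- k = 4: intervals 1–2, 2–3 and 3–4. The slot exists.
- k = 5: intervals 1–2, 2–3, 3–4 and 4–5. The slot exists.

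Section 4.6 requires the scan to be both during the course and after fraction 3. For k = 3 these conditions exclude each other.

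**4. Smaller inconsistencies**

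- Section 4.2 places both added scans during treatment; 4.6 and Appendix I place one during and one after.
- In Table 2 of 8.4, two rows follow from their factors: 7 × 0.61 × 2 = 8.54 and 28 × 0.08 × 4 = 8.96. The SBRT row does not: 5 × 0.61 × 2 = 6.10, but 3.05 is printed, which is 5 × 0.61. This is routine positioning dose, and no other sentence uses it.

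**The case against.** The strongest reply is that the four in section 4.3 is one stray word. The operative schedule, both calendars and the risk text agree on three, and staff working from Appendix I would find no fourth visit. The three in the summary of 8.4 may simply include the planning CT, in which case the 6% is right and only the wording is loose. This limits the practical ambiguity but does not remove it: 4.3 is a current, mandatory statement, and the summary in 8.4 can be read as agreeing with it. The substitution note does not help, because it changes who orders a scan and not how many are required.

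On the SBRT slot, the 3-to-5 range is written for SRT and the slot for SBRT, and no sentence equates the two. That deserves saying, but the protocol uses both terms for one category. Section 8.1 lists SRT where 4.6 lists SBRT, Table 2 of 8.4 labels the stereotactic row SBRT, and no separate SBRT fraction number appears. It is also true that a scan after a third and final fraction satisfies the words about fraction 3 in 4.6; it then fails the requirement that the scan fall during the course.

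Two limits stand. The share of 3-fraction courses is not given and could be small or nil. The link to the primary objective is also partly inferred: section 2.1 names no scan times, section 6.0 specifies no time-trend analysis, and the planning and follow-up scans would remain.

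**Conclusion.** The concern holds and should be fixed. The total is four in one place and three in the others. The added count is two in three places and three in one, unless that one includes the planning CT, in which case its wording is wrong instead. The difference in stated added dose is 6.0% against 4.0% of one fraction at about 4 cGy per scan. Any error in the 6%, taken as the dose from two or three added scans, overstates exposure, so the protocol's risk conclusion is unchanged.

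The SBRT slot is unavailable only in 3-fraction courses; 4- and 5-fraction courses can meet it. This part assumes that SRT and SBRT denote the same treatments. The schema diagrams at the front of the protocol could not be read in the text available and should be checked for the same points. The documents do not settle which count or which timing is intended.

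**What to change.** - Reconcile sections 4.2, 4.3, 4.4, 4.6, 8.4 and Appendix I to one total number of CTs, one number added to standard care, and one placement of the added scans.
- Reconcile the SBRT mid-course timing in 4.6 and Appendix I, Table 2, with the fraction range in 8.4. No schedule is proposed here; that choice belongs to the investigators.
- In the summary of 8.4, either restate the 6% for the agreed added count or change the wording so that it is clear which scans the figure covers.
- Reconcile the SBRT row of Table 2 in 8.4 with its own factors.

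The cost is a wording amendment to whichever of these sections the agreed schedule touches, one percentage or one word, and one table row. Design, sample and analysis are untouched.

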4.4 Other Imaging Studies

Complementary to the two additional CT scans proposed in this study all other patient imaging data will also be collected for our analyses. This data is part of the standard of care used in radiotherapy for cancer and they include MRI and PET-CT scans. MRIs and PET-CTs are very often ordered by the attending physicians for pre-treatment purposes, where they help delineate targets and OARs for treatment planning purposes. Furthermore, MRIs and PET-CTs can also be ordered by the treating doctors several weeks post-radiotherapy to assess tumor response, potential complications, and to assess treatment outcome.

4.5 Experimental Virtual Treatment Planning

The CT data acquired under this protocol will also be used for testing and development of our mass-based optimization methods. Those experimental plans will not be used for patient treatments. The plans used for patient treatment would be based on the standard of care described in section 4.3. Prospective data collection of 3D and 4D CT patient scans will be utilized for tallying DVH and DMH end-points and their relation to changes in pulmonary function, as well as studying interaction between tumor time-trending changes and DMH parameters in NSCLC, HNSCC, and prostate cases. All experimental mass-based treatment planning will be necessarily retrospective. Should a finding on one of the repetitive CT scans necessitate a change in plan or medical intervention, this will be at the discretion of the attending physician and will be performed according to the standard of care.

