1.2.3. Treatment Planning for Radiotherapy

Cancer patients are treated according to the standard of care with either conformal radiotherapy (3DCRT), intensity modulated radiotherapy (IMRT), volumetric modulated arc therapy (VMAT), or a linear accelerator (linac) based stereotactic radiation therapy (SRT). Treatment planning is performed with any combination of coplanar or non-coplanar fields to deliver the prescribed dose, while restricting the dose to the normal tissues to empirically determined dose levels. Field arrangements and plan parameter optimization are determined by

experienced planners to produce the optimal plan in accordance with volume definitions and attending physician prescriptions and goals.^{86, 127-137}

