6.0 DATA ANALYSES PLAN

This clinical imaging study will form a database for future research and development of 3D and 4D treatment planning approaches for different anatomical sites treated with radiotherapy. Statistical analyses will be used to assess the differences among standard of care, realized through DVHs, and our newly proposed mass-based optimizations and DMH evaluations. Those statistical analyses are powered to detect clinically significant differences in dosimetry and estimated clinical outcome endpoints between various proposed simulated treatment techniques. Significant changes include:

- Dosimetric: a dose variation between the different treatment planning approaches for normal tissue structures of more than 7%.
- Estimated clinical outcome: a $\geq 5\%$ variation of normal tissue toxicity using the generalized equivalent uniform dose (gEUD) metric and isoeffect parameters and analyses tools developed by the NCI funded R01 CA163370 research grant.

We will start with the null hypothesis that no difference between the treatment planning approaches is observed for the dosimetric and the estimated clinical outcome endpoints. Since patients are treated according to the standard of care and only their imaging information is used to estimate the potential outcome benefit of the new planning approaches, each patient serves as a control for themselves. Results will therefore be paired. The differences between the standard of care inverse optimization

and the proposed mass-based schemes for tumors will be tested using one-tailed paired *t*-tests, against a hypothesis that $\pm 3\%$ radiation dose differences in the tumors will not have an observable clinical significance. The differences between the optimization results on the remaining parameters for all healthy anatomical structures (within the radiation field) will be tested using standard two-tailed *t*-tests with the null hypothesis set to 0%. We anticipate an enrollment period of five years.

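### The paired planning comparison does not define its control plan; if the clinical treatment plan is used, the effect of the mass-based cost function is mixed with the effect of planning again

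*Combined protocol and SAP*

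**What the plan says.** Section 4.5 describes two kinds of plan. The mass-based plans are experimental: "All experimental mass-based treatment planning will be necessarily retrospective" and "Those experimental plans will not be used for patient treatments". The others are the plans delivered to patients: "The plans used for patient treatment would be based on the standard of care described in section 4.3". (Section 4.3 covers CT specifications; treatment planning is in 4.2.)

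Section 4.2 says of the delivered plans that "The treatment plan used for each patient will be based on analyses of the volumetric dose", including DVH analysis, and that "Field arrangements will be determined to produce the optimal plan in accordance with volume definitions". Section 1.2.3 adds, for standard care, "Field arrangements and plan parameter optimization are determined by" experienced planners working to the attending physician's prescription and goals.

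Section 6.0 explains the pairing as follows: "Since patients are treated according to the standard of care and only their imaging information is used to estimate the potential outcome benefit", each patient acts as their own control. The tumour test is introduced with "The differences between the standard of care inverse optimization", set against the mass-based schemes. Healthy structures are tested two-tailed against a null of 0%. A dosimetric change counts as significant when it exceeds 7%. Section 6.0 also calls the compared techniques simulated.

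Sections 4.2, 4.5 and 6.0 neither mention a volume-based plan re-optimised for research nor set conditions for matching the two plans of a pair.

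**The concern.** The planning comparison is meant to show what changing the cost function does to organ doses. That requires two plans that differ only in the cost function. A plan made for treatment and one made afterwards for research may also differ in planner, beam arrangement, objectives, number of iterations and effort. Pairing removes differences between patients; it does nothing about differences between the two planning processes within a patient.

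If planning a second time lowers organ dose under any cost function, the 0% null can be rejected with no mass-based benefit at all. A larger sample makes that more likely. At stake are the first study hypothesis (that mass-based optimisation reduces dose to normal tissue and organs at risk) and the planning comparison in section 6.0.

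**Working it through.** **Which plan is the control?** The evidence in the text points both ways.

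- *Towards the clinical plan.* Section 6.0 bases pairing on patients being treated by standard of care. The only standard-of-care plan that the protocol produces is the treatment plan of section 4.2. Section 4.5 lists treatment plans and mass-based plans and nothing else.
- *Towards a simulated DVH plan.* Section 6.0 calls the compared techniques simulated, names the comparator as a form of optimisation and not as the delivered plan, and says that only imaging information is used.
- *Left open on either reading.* Sections 4.6 and 8.1 include three-dimensional conformal (3DCT) patients, and section 1.2.3 lists conformal treatment separately from IMRT and VMAT. These patients may have no inverse-optimised treatment plan. Section 5.0 allows the treatment plan to be adapted during the course, without saying which plan would then be the control.

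**How large could the effect be?** There is no figure in the plan to reproduce: section 6.0 says the analyses are powered but gives no sample size, alpha, power or SD of the paired difference.

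Inputs from section 6.0: pairing, two-tailed test of healthy structures, null 0%, threshold 7%.

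Assumptions not in the documents: alpha 0.05; true mass-based effect zero; number of pairs n; SD of the paired percentage difference s; gain from re-planning alone b.

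The paired t statistic then follows a noncentral t distribution with n − 1 degrees of freedom and noncentrality δ = b√n / s. The chance of rejecting the null is P(|T| > t), where t is the 97.5% point of the central t distribution.

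| b | n | s | δ | t | P(reject) |
|---|---|---|---|---|---|
| 3% | 10 | 10% | 3√10/10 = 0.949 | 2.262 | 0.136 |
| 3% | 30 | 10% | 3√30/10 = 1.643 | 2.045 | 0.355 |
| 3% | 30 | 5% | 3√30/5 = 3.286 | 2.045 | 0.888 |
| 3% | 100 | 10% | 3√100/10 = 3.000 | 1.984 | 0.844 |
| 5% | 30 | 10% | 5√30/10 = 2.739 | 2.045 | 0.754 |
| 2% | 20 | 15% | 2√20/15 = 0.596 | 2.093 | 0.088 |

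With b = 0, which is what a fully matched control aims for, δ = 0 and the rate is 0.05 for every n and s. The two-sided rate is the same for a re-planning loss of the same size; only the direction of the false conclusion changes.

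**Against the 7% threshold.** With n = 30 and s = 10%, the standard error is 10/√30 = 1.826%. For b = 3%, the chance that the observed mean exceeds 7% is P(Z > (7 − 3)/1.826) = P(Z > 2.19) ≈ 0.014. For b = 5%, it is P(Z > 1.10) ≈ 0.14. Statistical significance is therefore much easier to reach by re-planning alone than the plan's own size criterion. A 3-point gain would still make up 3/7 = 43% of an observed 7% difference.

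**The case against.** The strongest reply is that section 6.0 never names the delivered plan as the control. It speaks of simulated techniques and of inverse optimisation, and section 1.2.1 frames the question as volume-based against mass-based cost functions. Conformal patients whose delivered plan was not inversely optimised could not supply such a comparator, which suggests that a simulated DVH plan was intended. This stands as far as it goes: a reader might infer that the control is the treatment plan, but the documents do not establish it. Equally, they do not provide for a simulated DVH plan or say how one would be matched.

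A second reply is that the differences between the plans are inferred. This also stands. No planner is named for the mass-based plans, and nothing says that beams, objectives or iterations differ. The point is that nothing requires them to be the same.

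A reader might also infer that any bias must favour the new method. The documents do not support that. Clinical plans come from experienced planners seeking the best plan, and an optimiser still under development could do worse. The opposite direction remains plausible because section 1.2.3 describes clinical planning as holding normal-tissue dose to set levels, while a plan made to test organ sparing has reason to go further.

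Finally, the first primary objective, whether dose-mass histograms (DMHs) predict response or toxicity better than DVHs, does not depend on this comparison. That is correct and limits the reach of the point.

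**Conclusion.** The point holds in conditional form. The plan does not define the control of its paired planning comparison, and it permits, and leans towards, a control that confounds the cost function with re-planning. If the clinical plan is used, a rejected 0% null cannot be attributed to mass-based optimisation.

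The percentages above show sensitivity and do not estimate the actual bias, because n, SD, alpha and the gain are all assumed. Within those assumptions a 3% gain produces false rejection in about 14% to 89% of studies, against a nominal 5%. It would rarely carry the observed mean past 7% (about 1% at n = 30, SD 10%). It would therefore go too far to say that modest re-planning gains alone would meet the plan's own criterion for a significant dosimetric change, although section 6.0 does not make that criterion a formal decision rule.

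The consequence is confined to hypothesis 1 and the section 6.0 planning comparison. This is a worthwhile, inexpensive improvement and not a fault in the study as a whole.

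**What to change.** In sections 4.5 and 6.0, define the control of each pair as a DVH-based inverse plan re-optimised for research. It should share the following with the mass-based plan, so that only the cost function differs:

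- CT and contours
- beam or arc geometry
- prescription and target-coverage normalisation
- corresponding objectives
- planner or planning script
- stopping rule

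Report the clinical plan as a secondary reference, and state which clinical plan is meant where treatment was re-planned during the course. This also gives 3DCT patients an inverse-optimised comparator. In the same edit, correct the reference in 4.5 so that it points to the section describing treatment planning.

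The cost is one extra computer plan per patient and a few sentences of text. It needs no patient contact and changes nothing in treatment. The matched control serves whichever comparator the investigators had in mind.
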